2. BACKGROUND

2.1 Study Disease

MCC is an aggressive skin cancer with a 5-year disease-associated mortality of 46% [[Lemos 2010](#)]. Nearly 50% of patients with MCC develop distant disease typically within 2 to 3 years of diagnosis. Systemic chemotherapy is commonly used, but is fairly toxic with limited, transient efficacy. The reported incidence of MCC has quadrupled in the past 20 years to an estimated ~1600 cases/year in the United States [[Hodgson 2005](#); [Albores-Saavedra 2010](#)]. This increasing incidence is partly due to improved detection using a specific IHC marker, cytokeratin-20, [[Moll 1992](#)] but may also be due to the higher prevalence of known risk factors for MCC: chronic T-cell immune suppression [[Penn 1999](#); [Engels 2002](#); [Heath 2008](#)] and the number of Caucasians over 50 years of age with extensive prior sun exposure [[Heath 2008](#)]. Despite its growing health impact and aggressive behavior, very few clinical trials have focused on this disease. There is an unmet need for biology-driven therapy in MCC.

MCC is causally associated with the MCPyV [[Feng 2008](#), [Houben 2010](#), [Rodig 2012](#)]. The viral T-Ag oncoproteins, present in approximately 80% of MCC tumors, are required for ongoing tumor growth [[Houben 2010](#)]. The cellular immune response is strongly linked to outcome in MCC. Specifically, intratumoral CD8+ lymphocyte infiltration is associated with improved survival independent of stage at presentation [[Paulson 2011](#)]. MCPyV-specific T cells have been isolated from the blood and tumors of patients with MCC and track with disease burden.

PD-1 is likely playing a key role in MCC immune evasion in many patients [[Afanasiev 2013](#)]. The PD-1 receptor-ligand interaction is a major pathway hijacked by tumors to suppress immune control. The normal function of PD-1, expressed on the cell surface of activated T cells is to downmodulate unwanted or excessive immune responses, including autoimmune reactions. Over 90% of MCPyV-specific T cells express PD-1. The fact that PD-1 expression is high on these T cells, in combination with frequent expression of related T-cell immunoglobulin mucin-3 (TIM-3), suggests T-cell exhaustion/dysfunction is prevalent. Although these virus-specific T cells are present in many patients with MCC, they often fail to control progression of MCC, potentially due to immune evasion and exhaustion.

2.1.1 *Merkel cell polyomavirus (MCPyV) and MCC*

The discovery of the MCPyV in 2008, and its causal association with ~80–95% of

MCCs, [[Feng 2008](#); [Houben 2010](#); [Rodig 2012](#)] has provided new insight into MCC pathogenesis and underscores the importance of characterizing MCPyV-specific immune responses. MCC typically requires persistent expression of immunogenic polyomavirus T-Ag oncoproteins for ongoing growth and survival [[Houben 2012](#)]. The necessary and persistent [[Houben 2010](#)] expression of MCPyV T-Ag oncoproteins in MCC tumors provides a unique opportunity, not available for most cancers, to study antitumor immunity and immune evasion by assessing responses against virus-derived, tumor-specific antigens.

2.1.2 ***Cellular Immunity and MCC***

There is substantial evidence that cellular immune function is important for survival from MCC. Intratumoral CD8+ lymphocyte infiltration is associated with improved survival as first reported by the [name] group [[Paulson 2011](#)]. This association has been validated in a second, large, independent cohort [[Sihto 2012](#)]. In a similar vein, patients with profound T-cell dysfunction, [[Penn 1999](#); [Engels 2002](#); [Heath 2008](#)] such as hematologic malignancies, HIV/AIDS, and immunosuppressive medications for autoimmune disease or transplant, have 10- to 30-fold increased MCC risk, and MCC sometimes spontaneously regresses after improvement in immune function in those patients. Moreover, patients with systemic immune suppression have decreased median survival in MCC independently of stage [[Paulson 2013](#)].

2.1.3 ***Cellular Immune Response against MCPyV in MCC***

The persistent expression of MCPyV oncoproteins in MCC provides a unique opportunity to characterize immune evasion mechanisms in this cancer. Patients with MCPyV-positive MCC tumors frequently have T cells specific for these persistently expressed oncoproteins [[Iyer 2011](#)]. We hypothesized that these MCPyV-specific T cells, although present in the blood of patients with MCC, were unable to eliminate MCC tumors, either because they were dysfunctional and/or due to the other immune evasion mechanisms. We determined the presence and functional status of tumor-infiltrating lymphocytes (TIL, n=7) and virus-specific peripheral blood T cells from 18 patients with MCC and 10 control patients. MCPyV-specific CD8 T cells were detected directly ex vivo from the blood of 7 of 11 (64%) patients with MCPyV-positive tumors. In contrast, 0 of 10 control patients had detectable levels of these cells in their blood ($P<0.01$) [[Afanasiev 2013](#)]. MCPyV-specific T cells in serial blood specimens increased with MCC disease progression and decreased with effective disease therapy. Because T-cell number increases with disease burden, there is a need for careful interpretation of immunotherapy efficacy data aimed at increasing tumor-specific T-cell frequency. The presence and expansion of MCC-specific T cells with increasing tumor burden is highly suggestive that tumor immune escape mechanisms are active in MCC.

2.1.4 ***Active Immune Evasion Mechanism in MCC***

In MCC tumors, PD-L1 expression within the tumor microenvironment has been observed and is positively correlated with the number of infiltrating CD8 lymphocytes using both histologic and mRNA-based analyses in independent cohorts [[Afanasiev 2013](#); [Lipson 2013](#)]. Over 90% of MCPyV-specific T cells express PD-1 (as compared with approximately 30% of all CD8+ T cells, approximately 50% of cytomegalovirus [CMV]-specific T cells, and approximately 80% of Epstein-Barr virus [EBV]-specific T cells).

Furthermore, PD-1 surface expression on MCPyV-specific T cells is >2-fold higher compared to EBV- or CMV-specific T cells and its ligand, PD-L1, was present in 9 of 13 (69%) of MCC tumors [Afanasiev 2013]. PD-1 and TIM-3 are simultaneously co-expressed on the majority of MCC-specific T cells, a combination that is often associated with dysfunction [Fourcade 2010; Sakuishi 2010]. T-cell dysfunction mediated by surface expression of these inhibitory molecules on T cells may, at least in part, explain why MCC tumors grow despite the presence of an immune response. These findings are consistent with prior reports indicating that chronic antigen exposure to tumor and viral antigens leads to the upregulation of inhibitory receptors such as PD-1 and TIM-3, which results in reversible T-cell dysfunction [Barber 2006; Jones 2008; Fourcade 2010; Greenough 2010; Wherry 2011]. In contrast to prior studies of virus- or tumor-specific CD8-T cells that show upregulation of PD-1 with acute infection [Greenough 2010] or with increasing tumor stage, [Kronig 2012] PD-1 expression on MCPyV-specific T cells was maintained at high levels throughout the MCC disease course even during declining T-cell absolute numbers during remission [Afanasiev 2013].

In melanoma, most circulating melanoma-specific CD8 T cells have been reported to be functionally active, whereas those derived from tumor lesions are functionally tolerant [Zippelius 2004]. In contrast, in MCC, T cells derived from the blood and tumor compartments have similar phenotypic profiles, both indicative of T-cell dysfunction [Afanasiev 2013]. Activation and inhibitory receptors tend to be induced simultaneously on MCC-specific T cells, consistent with chronic antigen exposure likely triggering immune tolerance, in agreement with prior studies of HIV-specific CD8 T cells [Trautmann 2006; Sauce 2007].

PD-1 upregulation on tumor-targeting CD8 T cells is particularly relevant if its ligand is expressed within the tumor microenvironment, which can lead to inhibitory pathway activation. PD-L1 is selectively expressed on many tumors [Hamanishi 2007; Zou 2008; Hino 2010] and on cells within the tumor microenvironment [Curiel 2003] and blockade of the PD-1/PD-L1 pathway has been recently shown to effectively induce durable tumor regression and stabilization of disease in a subset of several diverse types of cancer [Sakuishi 2010; Fisher 2012].

In summary, MCPyV-specific T cells: (1) dynamically correlate in frequency with clinical disease burden and with antibodies against the viral oncoprotein (T-Ag), (2) co-express markers of exhaustion, PD-1 and TIM-3, at far higher levels than T cells specific for other common human viruses such as EBV, (3) display minimal interferon gamma (IFN- γ) production in response to cognate peptide, which can be augmented after culture with inhibitory receptor blocking agents, and (4) are likely to encounter the relevant inhibitory receptor ligand, PD-L1, within the MCC tumor microenvironment.

2.1.5 *MCC as a Candidate for Testing MK-3475*

MK-3475 is a potent and highly selective humanized monoclonal antibody (mAb) of the immunoglobulin G4 (IgG4)/kappa isotype designed to directly block the interaction between PD-1 and its ligands, PD-L1 and PD-L2. This blockade enhances functional activity of the target T cells to facilitate tumor regression and ultimately immune rejection.

The expression of PD-1 and PD-L1 support the testing of the antibody to PD-1 (anti-PD-1) as a targeted approach to overcome tumor immune evasion mechanisms in MCC. The direct relationship of T-cell and antibody responses to the burden of MCC provide clinical biomarkers of disease status and may also serve as a potential indicator of response to anti-PD-1.

2.1.6 ***Orphan Disease with Important Unmet Medical Needs***

Despite the strong rationale for investigation of immunotherapy in this virus-associated cancer, there are no systemic immune therapies approved or currently being investigated [Miller 2013]. The chances of successful immunotherapy for MCC are fairly high, in part due to its obligate viral protein expression [Houben 2010].

2.1.7 ***Treatment with Cytotoxic Chemotherapy***

There are no FDA-approved therapies for MCC. However, systemic chemotherapy has been commonly used to manage metastatic MCC, despite toxicity and limited, transient efficacy. The National Comprehensive Cancer Network (NCCN) Merkel Cell Carcinoma Guidelines Version 1.2012 [Page MS-4] states “Data are insufficient to assess whether chemotherapy regimens improve either relapse-free or overall survival in MCC patients with distant metastatic disease.” Data from patients treated by the [name] group at the Fred Hutchinson/University of Washington Cancer Consortium (FH/UW Consortium) shows that responders have a prolonged PFS compared to nonresponders, but without randomized data for the disease there is no firm evidence that chemotherapy improves OS.

If chemotherapy is used, the NCCN recommends cisplatin or carboplatin with or without etoposide [NCCN 2012]. Most patients with metastatic MCC will respond to chemotherapy, but will progress between 3 and 5 months and have a median time to death of 9 months after initial metastasis. Accordingly, the NCCN concludes “Clinicians should exercise independent medical judgment in choosing the chemotherapeutic regimen. Although the NCCN panel recognized that MCC is a rare disease that precludes robust randomized studies, enrollment in clinical trials is encouraged whenever available and appropriate.”

The MCC team at the FH/UW Consortium has analyzed data from 58 patients in the Seattle cohort who developed distant metastatic disease, received first-line chemotherapy, and had evaluable metastatic lesion(s) that were not also treated with radiation or surgery (allowing the effects of chemo-mono-therapy to be evaluated). The median time to progression following chemotherapy in the Seattle cohort with “-platin”-based regimens was 98 days for the whole treated population and 145 days for the responding patients (details below).

TOTAL PATIENTS RECEIVING FIRST-LINE CHEMOTHERAPY (n = 58)

Complete response (CR): 8 of 58 (14%)
Partial response (PR): 24 of 58 (41%)
Stable disease (SD): 4 of 58 (7%)
TOTAL CR/PR/SD: 36 of 58 (64%)

Total Progressed at time of analysis (November 2013): 56 of 58 (97%)
Total not progressed 2 of 58 (1 CR and 1 PR) (3%)

Time to progression among all 58 evaluable chemo-treated cases:
50% progressed (Median time from start of chemotherapy) = 98.5 days
80% progressed = 222 days
90% progressed = 290 days
95% progressed = 428 days

Note: the progression from 0% to 95% looks like a straight line on a semi-log plot with no evidence of a plateau.

TOTAL PATIENTS THAT RESPONDED TO FIRST-LINE CHEMOTHERAPY (CR/PR/SD) (n = 36)

Progressed: 34 of 36 (94.4%)
Not progressed: 2 of 36 (5.5%) (1 CR and 1 PR)

Time to progression among “chemo responders”:
50% (median) progressed 145 days
 50% (median) of CR patients = 303 days
 50% (median) of PR patients = 145 days
 50% (median) of SD patients = 132 days
80% progressed = 288 days
90% progressed = 316 days
94.4% progressed = 466 days

[figure not shown]

Figure 1: First-line chemotherapy and progression-free survival (PFS) in MCC patients with metastatic disease.

These data are derived from 58 patients in the Seattle cohort who developed distant metastatic disease, received first-line chemotherapy, and had evaluable metastatic lesion(s) that were not also treated with radiation or surgery (allowing the effects of chemo-mono-therapy to be evaluated). The vertical axis represents the number of DAYS between the start of first-line chemotherapy and progression (or death). Etoposide was combined with a “platin” in the 40 cases shown as blue bars. Among these 40 cases, the “platin” was carboplatin in 29 cases and cisplatin in 11. Patients 57 and 58 (asterisks) are the only ones who did not progress on chemotherapy or die, as of most recent data. Median PFS was 98.5 days from start of chemotherapy to progression or death. These 58 patients are a subset of the 179 patients we recently reported in which median OS was 289 days (9.5 months) from the date when distant disease was identified (Figure 3).

[figure not shown]

Figure 2: Progression-free survival (PFS) in MCC patients with metastatic disease, treated with first-line chemotherapy and responded with CR, PR, or SD.

These data represent the 36 “chemo responders” among the full cohort of 58 chemotherapy-treated patients in the Seattle cohort shown in Figure 1. Specifically, these 36 patients developed distant metastatic disease, received first-line chemotherapy, and achieved a complete or partial response. The vertical axis represents the number of DAYS between the start of first-line chemotherapy and progression (or death). Median PFS was 145 days from start of chemotherapy to progression or death. These 36 patients are a subset of the 179 patients with distant disease shown in Figure 3.

[figure not shown]

Figure 3: Disease-specific survival in patients who developed metastatic MCC.

Survival data are shown from 179 patients with metastatic MCC who were followed at the FH/UW Consortium [Miller 2013]. Median survival was 289 days from initial diagnosis of metastatic disease. When measured starting at the time of developing metastatic disease, there were no significant differences in survival based on the initial stage at presentation (data not shown). However, stage greatly influenced the likelihood of and median time to developing metastatic disease.

Given that cytotoxic chemotherapy-induced responses are typically very short in duration and there is no proven beneficial effect of cytotoxic chemotherapy on OS, the proposed trial will be conducted in chemotherapy-naïve patients and patients who received prior adjuvant chemotherapy more than 6 months before study participation. The likelihood of success with MK-3475 should be greater if given to patients who are immunocompetent (more likely in chemotherapy-naïve patients). In general, response rates and DOR are expected to be diminished with each subsequent line of therapy. This was indeed the case for MCC, with median PFS of 98 days in first line that decreased to 61 days in second-line chemotherapy, and overall response rate that fell from 54% to 23% in second line (Iyer, [name], et al, unpublished). Finally, the antitumor activity of PD-1 in several malignancies, melanoma, renal cell carcinoma (RCC), and non-small cell lung cancer (NSCLC), is greater than the efficacy of chemotherapy in MCC, further supporting the study of anti-PD-1 as first-line therapy. Subjects who are treated with anti-PD-1 therapy are therefore unlikely to give up a substantially meaningful benefit from front-line chemotherapy. This will be explained to patients in detail in the consent form.

Radiation therapy is commonly used to treat MCC, but is not considered to be a systemic therapy in this protocol. Radiation therapy is considered useful as a treatment option for all stages of MCC [NCCN 2015]. For radiation as adjuvant to surgery, a meta-analysis comparing surgery alone with surgery plus adjuvant radiation revealed that the use of adjuvant radiation after complete excision lowered the risk of local and regional recurrences [Lewis 2006]. For radiation to the primary tumor or regional lymph nodes, a review of 83 cases diagnosed between 1992 and 2004 showed that administration prolonged time to recurrence and survival [Jabbour 2007]. For primary therapy, radiation is considered acceptable in select cases when complete excision is not feasible or refused by the patient. An Australian retrospective review of 43 patients reported an in-field tumor control rate of 75% using radiation alone [Veness 2010]. Radiation may also be

useful in the palliative setting.

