1.3 Exploratory Objectives

To determine the immune correlates of the clinical activity of MK-3475

The endpoints will include immunohistochemical (IHC) and gene expression analysis, whole exome sequencing, and neoantigen identification focusing on delineating the immune components and immunologic milieu within the tumor before therapy. The IHC analytes will include, but are not limited to Merkel cell polyomavirus (MCPyV) tumor antigen (T-Ag), programmed cell death 1 (PD-1), and its ligand 1 (PD-L1), CD8, CD3, CD68, CD45, and CD56. In addition, MCPyV viral DNA will be quantified in the tumor and T cell receptor sequencing in tumor infiltrating lymphocytes (TIL) will be performed where pre- and post-treatment biopsies

are available. Cellular and humoral MCPyV-specific immune responses will be assessed with Enzyme-Linked ImmunoSpot (ELISpot) serology assays in blood samples at baseline, after initiating MK-3475 therapy, and correlated with clinical responses over time. Among patients with corresponding major histocompatibility complex (MHC)-peptide tetramers, pre-and post-treatment samples of circulating MCPyV-specific CD8 T cells will be isolated by flow cytometry and subjected to deep immunophenotyping by messenger RNA (mRNA) expression analysis.

Hypothesis: MK-3475 will enhance functional activity of MCC-specific lymphocytes and facilitate tumor regression. Thus, the clinical endpoints associated with tumor regression and durability of response will be correlated with the pretreatment levels and type of immune cell infiltration in the tumor, PD-1 and PD-L1 expression and association in the tumor, or systemic measures of immune response to tumor-specific viral MCPyV antigens.

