Key questions that these correlative studies will address include: (1) Will the surface marker phenotype and/or transcriptional state of a patient's "exhausted" tumor-specific PD-1+ CD8 T cell predict response to MK-3475?; (2) Does the surface marker phenotype and/or transcriptional state of a patient's "exhausted" tumor-specific PD-1+ CD8 T cells correlate with features such as CD8 infiltration in the pretreatment tumor? And, are these features modulated with MK-3475 treatment?; and (3) Will PD-1+ T cells from nonresponding patients be characterized by a specific pattern of gene regulation, mutanome landscape or neoantigen array compared to those of responders? Specifically, are additional counter-regulatory immune modulators expressed to compensate for PD-1 blockade? If so, these secondary counter-regulatory immune modulators may represent relevant targets to overcome resistance to PD-1 therapy.

ELISpot analysis will be performed by the CITN Immune Monitoring Laboratory under the direction of [name]. ICS analyses will be performed by the laboratory of [name] at FHCRC.

2.5.4 ***Merkel Cell Polyomavirus–Specific Antibody Responses—Laboratory Correlative Studies #6***

Because antibody titers for the T-Ag oncoprotein are a marker of disease burden and immune responsiveness to the virus, we will also test for these antibodies at baseline [[Paulson 2010](#)]. If positive, this assay will be carried out on serum collected at the time of scans. We anticipate that 50% of patients will make antibody to the MCPyV oncoprotein. Key questions include (1) Are seropositive patients more likely to respond to anti-PD-1? and (2) Do antibody titers provide greater or different insights into responses than gold-standard imaging studies? In several cases, rises in oncoprotein antibody have occurred before detection of disease by CT and may herald early immune recognition of recurrent disease. This serologic assay will be performed by Luminex and carried out by the CLIA-certified Clinical Immunology Laboratory, Department of Laboratory Medicine, at the UW in conjunction with [name] lab.

2.5.5 ***Quantification of PBMC and T-cell Subsets—Laboratory Correlative Study #7***

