Nonmeasurable disease. All other lesions (or sites of disease), including small lesions (longest diameter < 10 mm or pathological lymph nodes with ≥ 10 to < 15 mm short axis), are considered nonmeasurable disease. Bone lesions, leptomeningeal disease, ascites, pleural/pericardial effusions, lymphangitis cutis/pulmonitis, inflammatory breast disease, and abdominal masses (not followed by CT or MRI), are considered as nonmeasurable.

Note: Cystic lesions that meet the criteria for radiographically defined simple cysts should not be considered as malignant lesions (neither measurable nor nonmeasurable) since they are, by definition, simple cysts.

“Cystic lesions” thought to represent cystic metastases can be considered as measurable lesions, if they meet the definition of measurability described above. However, if noncystic lesions are present in the same patient, these are preferred for selection as target lesions.

Target lesions. All measurable lesions up to a maximum of 2 lesions per organ and 5 lesions in total, representative of all involved organs, should be identified as **target lesions** and recorded and measured at baseline. Target lesions should be selected on the basis of their size (lesions with the longest diameter), be representative of all involved organs, but in addition should be those that lend themselves to reproducible repeated measurements. It may be the case that, on occasion, the largest lesion does not lend itself to reproducible measurement, in which circumstance the next largest lesion that can be measured reproducibly should be selected. A sum of the diameters (longest for non-nodal lesions, short axis for nodal lesions) for all target lesions will be calculated and reported as the baseline sum diameters. If lymph nodes are to be included in the sum, then only the short axis is added into the sum. The baseline sum diameters will be used as reference to

further characterize any objective tumor regression in the measurable dimension of the disease.

Non-target lesions. All other lesions (or sites of disease) including any measurable lesions over and above the 5 target lesions should be identified as **non-target lesions** and should also be recorded at baseline. Measurements of these lesions are not required, but the presence, absence, or in rare cases unequivocal progression of each should be noted throughout follow-up.

11.1.3 **Methods for Evaluation of Measurable Disease**

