PFS and OS by the following biomarker categories: 
 • pre-therapy CD8+ • pre-therapy CD3+ T-cell infiltration in tumor • pre-therapy PD-1 and PD-L1 expression in tumor, 
 • * pre-therapy immune response to MCPyV 	Descriptive statistics	Eligible subjects who receive at least 1 dose of treatment	censored at last assessment

ORR by the following biomarker categories:
 
 • pre-therapy CD8+ • pre-therapy CD3+ T-cell infiltration in tumor • pre-therapy PD-1 and PD-L1 expression in tumor, 
* pre-therapy immune response to MCPyV
	
Descriptive statistics
	
Eligible subjects who receive at least 1 dose of treatment
	
Missing value considered nonresponder

--	-------------------------------	---	--

Note: PD after 1 or more missed visits will be counted as PD as of the date of documented disease progression. An additional sensitivity analysis will be performed where subjects with 2 or more missed visits before progression will be censored at the last disease assessment before the ≥ 2 missed disease assessments.

13.5.2 *Statistical Methods for Safety Analyses*

Safety and tolerability will be assessed by clinical review of all relevant parameters including adverse experiences, laboratory tests, vital signs, and ECG measurements.

Adverse experiences will be summarized as counts and frequencies by toxicity grade. Summary statistics (median and range) for time to onset of first drug-related toxicity will be provided.

Laboratory assessments, vital signs, and other safety endpoints will be summarized using descriptive statistics as appropriate.

13.5.3 *Summaries of Baseline Characteristics, Demographics, and Other Analyses*

The number and percentage of subjects enrolled, and the primary reason for discontinuation will be displayed. Demographic variables (such as age) and baseline characteristics will be summarized either by descriptive statistics or categorical tables. No statistical hypothesis tests will be performed on these characteristics.

13.6 **Multiplicity**

The treatment comparison will be tested at one sided 5% alpha level and no multiplicity adjustment will be applied.

13.7 **Sample Size/Accrual Rate and Power Calculations**

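### Table 13.1 describes ORR, PFS and OS by pre-therapy MCPyV immune response without accounting for tumor burden, although the protocol says those immune measures track burden

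*Combined protocol and SAP*

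**What the plan says.** **Immune measures and burden.** Section 2.1.3 says "MCPyV-specific T cells in serial blood specimens increased with MCC disease progression and decreased with effective disease therapy" and concludes that "there is a need for careful interpretation of immunotherapy efficacy data aimed at increasing tumor-specific T-cell frequency". The summary closing section 2.1.4 links T-cell frequency both to clinical burden and to T-Ag antibody. Section 2.5.4 gives its reason for baseline serology as: "Because antibody titers for the T-Ag oncoprotein are a marker of disease burden and immune responsiveness to the virus". One titer therefore carries two meanings.

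**Questions asked.** Section 2.5.4 asks "Are seropositive patients more likely to respond to anti-PD-1", and whether titers give different insight from imaging. The hypothesis in section 1.3 relates tumor regression and durability to, among other things, systemic immune response to viral antigens. Sections 1.3 and 13.2.3 add that ELISpot and serology results will be measured at baseline and "after initiating MK-3475 therapy, and correlated with clinical responses over time", with no method named.

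**Planned analysis.** Table 13.1 lists "pre-therapy immune response to MCPyV" as a category for ORR and for PFS and OS, with descriptive statistics as the method. It does not say which assay defines the category. Section 13 has no burden covariate or stratum, and section 13.8 marks stratification factors as not applicable. The only covariate model, in 13.5.1.1, is a missing-data fallback for overall ORR. The opening of section 13 rules out a separate SAP.

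**Burden data.** Under section 11.1.2 the sum of diameters "for all target lesions will be calculated and reported as the baseline sum diameters".

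**The concern.** At baseline, a high virus-specific T-cell response or antibody titer may mean stronger immunity, more tumor, or both. If patients with more tumor also do worse, the high-marker group carries a handicap unrelated to immunity. The table would then understate a real benefit, or show a deficit where the marker does nothing. Burden should vary widely, because section 3.1.1 admits both recurrent locoregional and metastatic disease.

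At stake is the reading of the virus-specific immune correlates, which may guide later biomarker or regimen choices. Confounding distorts a descriptive comparison as much as a formal test.

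**Working it through.** **1. The plan's own figure.** None is given for the biomarker analyses. The only design figures (type I error 0.10, power 0.90; exact calculation 0.093 and 0.903) belong to the two-stage ORR test and play no part here.

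**2. Inputs.** From the documents: n = 50 (13.7); about 50% antibody-positive (2.5.4), so about 25 patients; about 25% tetramer-evaluable (2.5.3.2), so 0.25 × 50 = 12.5, or 12 to 13 patients; ELISpot/ICS in all patients (2.5.3.3). Assumed, because the documents give neither: the strength of the marker-burden link and of the burden-outcome link.

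**3. Exact calculation for serostatus.** Half the patients have high burden. Seropositivity is s_H in high and s_L in low burden, with s_H + s_L = 1, so overall prevalence is 50%. Response in low-burden seronegative patients is 60% (odds 1.5, assumed). Odds elsewhere are 1.5 × (burden OR if high) × (marker OR if positive). Then:

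- response if seropositive = s_H × r(high, pos) + s_L × r(low, pos)
- response if seronegative = s_L × r(high, neg) + s_H × r(low, neg)

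Example with no marker effect, 70/30, burden OR 0.3: r(high) = 0.45/1.45 = 0.310. Seropositive: 0.7 × 0.310 + 0.3 × 0.6 = 0.397. Seronegative: 0.3 × 0.310 + 0.7 × 0.6 = 0.513. Apparent OR = (0.397/0.603)/(0.513/0.487) = 0.63.

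| s_H / s_L | Burden OR | True marker OR | Response, pos v neg | Apparent OR |
|---|---|---|---|---|
| 60/40 | 0.5 | 2 | 66.0% v 53.1% | 1.71 |
| 70/30 | 0.2 | 2 | 48.75% v 48.92% | 0.99 |
| 80/20 | 0.2 | 2 | 45.0% v 52.6% | 0.74 |
| 60/40 | 0.5 | 1 | 49.7% v 53.1% | 0.87 |
| 70/30 | 0.3 | 1 | 39.7% v 51.3% | 0.63 |
| 80/20 | 0.2 | 1 | 30.5% v 52.6% | 0.39 |

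With burden OR 1 the apparent OR equals the true one. With no marker-burden link (50/50) and burden OR 0.2, a true OR of 2 appears as 1.81; that part is non-collapsibility of the odds ratio, not confounding.

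**4. Simulation with a continuous marker.** n = 50, 1,500 runs per setting. Burden b is standard normal, marker m = ρb + √(1−ρ²)e, and logit P(response) = −0.8b + γm. Logistic fits with and without b:

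| ρ | γ = 0: OR without / with b | γ = 0: share p < 0.05 without / with b | γ = 0.4 (OR 1.49): OR without / with b | γ = 0.4: share p < 0.05 with b |
|---|---|---|---|---|
| 0.3 | 0.81 / 1.02 | 10% / 5% | 1.15 / 1.52 | 20% |
| 0.5 | 0.69 / 1.01 | 22% / 5% | 1.01 / 1.56 | 18% |
| 0.7 | 0.58 / 0.98 | 39% / 3% | 0.86 / 1.56 | 14% |

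With the burden coefficient at 0 and no marker effect, the unadjusted share is 3% to 5%. PFS and OS were not simulated; the same reasoning applies.

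**5. Imperfect burden measure.** The baseline sum covers at most 5 target lesions, 2 per organ (11.1.2). Step 4 was repeated (2,000 runs) adjusting for a proxy assumed to carry 50% to 70% of burden variance. With γ = 0 the adjusted OR is 0.68 to 0.92, and p < 0.05 occurs in about 4% to 15% of runs (up to about 20% with burden coefficient −1.0). Nearly all of the excess is in the unfavorable direction. Without adjustment, a spurious favorable result appears in at most about 0.5% of runs.

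**6. Tetramer subset.** At n = 12 the adjusted logistic model has essentially no power, and about 11% of fits were unusable.

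**7. On-treatment correlations.** Section 11.1.4.1 defines PR as at least a 30% fall in the target-lesion sum and PD as at least a 20% rise. Conditioning on the concurrent sum therefore conditions on the response itself.

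**The case against.** **These are exploratory descriptions by category.** This stands. No test, power claim or continuous-marker model is planned, so the significance rates above illustrate bias and are not properties of the plan.

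**No document says that burden predicts outcome on MK-3475.** This stands. The serial evidence in 2.1.3 is within-patient, and no between-patient baseline correlation is given. If either link is absent there is no confounding. Showing both estimates lets readers see how far burden matters in these data.

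**Whether seropositive patients respond more often is a marginal question.** Partly right: the unadjusted figure answers it as worded and should stay. Bias enters when the figure is read as an effect of immunity, which is the hypothesis in section 1.3.

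**Stronger readings a reader might infer.** One is that section 13 flouts the protocol's own warning. Section 2.1.3 asks for care in interpreting efficacy data where T-cell frequency is the target; the efficacy endpoints here are RECIST response, progression and survival. Another is that the over-time correlations are merely circular and should be adjusted for the sum of diameters at each scan. The documents do not support that: the sum defines response, and for the question of whether titers add to imaging, tracking burden is the subject of study.

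**Conclusion.** The gap is real and confined to exploratory analyses. The protocol says MCPyV T cells and T-Ag titers track burden, and Table 13.1 takes no account of it. If higher burden worsens outcome, the bias runs against the marker. Over the links tried, a true OR of 2 appears as 1.71 to 0.74, and a true OR of 1 as 0.87 to 0.39. Full reversal needs strong links on both sides, and an invented benefit is not the expected error. All sizes depend on assumed links and are illustrative only. Adjusting for the baseline sum reduces the bias without removing it, and precision stays low: 14% to 20% power for OR 1.49 per SD even with burden measured perfectly. A reader might infer that the trial's efficacy findings are in doubt; they are not, because ORR, PFS, DOR and OS overall do not use these markers.

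**What to change.** - **Baseline ELISpot/ICS and antibody measures:** add to Table 13.1 an exploratory logistic estimate for ORR and Cox estimates for PFS and OS, with log baseline sum of target-lesion diameters as covariate. Report them with confidence intervals beside the unadjusted figures. State that the sum omits non-target and nonmeasurable disease, so residual confounding remains.
- **Tetramer measures (about 12 to 13 patients):** keep descriptive.
- **On-treatment measures (1.3, 13.2.3):** do not adjust for the concurrent sum. Where the aim is to predict later outcome, use the marker value at one fixed early landmark, count outcome from there, and adjust for baseline burden. Study calendar footnote c already schedules a research draw at Cycle 2, before the week-13 scan. Serial titers are run only in baseline-positive patients (2.5.4), so about 25 would contribute.
- **Titers compared with imaging:** leave unadjusted.

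**Cost:** a few lines in section 13, no new data, and one extra parameter in a small exploratory model. Section 13 already allows changes to exploratory analyses to be listed and explained in the study report.
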